In-Home Technology for Caregivers of People With Dementia and Mild Cognitive Impairment: Wearables

Unique Protocol ID: 1247267250000-4

Secondary IDs: 2SB1AG059458-04A1

Identifiers:NCT05159557

Document Date: July 12, 2023

Pre-Screening Procedures:

Wearable Homes caregivers may be recruited through caregiver organizations (e.g., Alzheimer's Association, clinics (e.g., Nebraska Healthcare), other locations where caregivers gather/visit (e.g., support groups, senior centers), and media (e.g., print, social, digital). We have created a flyer/email script for these organizations to use that describes the research study and introduces the in-home technology, as well as a physical flyer to be posted in physical locations caregivers are likely to frequent. All recruitment materials describe the general nature and goals of the research and provide information about what should be expected if they participate. The Berkeley research team is listed as the source for additional information and addressing questions in all materials.

Initial Encounter:

Interested caregivers will be directed to an online website to learn more about the study and complete a screening questionnaire to determine eligibility. Caregivers must 1) be fluent/literate in English, 2) reside in the US and live with the person they are providing care for, 3) primarily use a smartphone (iPhone or Android), and 4) have WiFi internet service. Interested caregivers will also give their contact information for enrollment, as well as complete the consent to participate. Once a caregiver has been determined as eligible and enrolled through the website, a member of the Berkeley Psychophysiology Laboratory team will assess the capacity of the PWD to give consent to be in the study as a secondary subject. Once PWD consent is obtained either on their own, or through surrogate consent, caregiver participants will be sent a link to complete a set of questionnaires. Once PWD consent is obtained, People Power will mail the Presence Caregiver system to the caregivers for self-installation. People Power will be available to schedule virtual self-installation sessions if caregivers want by email or phone. Additional technical support for the system is available by email and phone during the course of the study.

Consent:

Participants will give consent online through the study website. Online consent requires participants to click on a box stating, "By clicking here, I indicate that I have read the above consent form and agree to take part in the research." Individuals receiving care (PWD) are asked to consent to participation as secondary subjects in order for information about them to be used for research purposes. In order to assess a patient's ability to consent to participation, a member of the research team will conduct a phone conversation with both caregiver and patient. The purpose of this conversation is to provide information about the study (e.g., participation responsibilities, compensation information, etc.) and to assess the PWDs cognitive capacity to consent for themselves using UCLA's "Decision-Making Capacity Assessment Tool." More specifically, a member of the Berkeley research team will determine the PWDs ability to 1) understand relevant study information, 2) ability to appreciate the situation and consequences of the study, 3) ability to rationalize or reason information presented, and 4) ability to make their own decision to participate in the study. If the investigator's evaluation is that the PWD can provide consent (i.e., the answer to questions 8 and 9 on the Assessment Tool are both "yes") the PWD will be asked to complete their own consent form via Qualtrics. If the PWD is judged to have diminished capacity (i.e., the answer to questions 8 or 9 are "no") then the caregiver will be asked to provide surrogate consent if the patient assents. Here, caregivers will be informed to the

nature of their decision during the study including patient's participation and decision to participate in certain procedures for the patient in order to ensure that the caregiver will be willing to undertake these on-going responsibilities. In addition, caregivers will be asked to identify a witness who will be willing to provide a bystander signature when they are completing the Self-Certification of Surrogate Decision Maker Form.

Baseline Outcome Assessment:

Once consent procedures are complete, caregivers receive a Qualtrics link with their initial questionnaire. Identical Qualtrics questionnaires will be sent via email to caregivers in both research conditions at baseline, 3 months, and 6 months. The three sets of questionnaires will be identical, except the baseline questionnaire will also include a contact information form and "Information about person receiving care."

Randomization:

Sixty caregivers will be randomly assigned to the "active in-home technology" condition of the system and the remaining 60 caregivers will be assigned to the "control" condition. Randomization of participants in each group will be determined by People Power employees after the consent process.

Outcome Measures:

All caregivers—regardless of randomized study condition—complete questionnaires on three separate occasions during this study: baseline, 3-months, 6-months. The four outcome measures are: (a) Zarit Burden Interview-Short Form, a questionnaire measuring caregiver burden (Zarit, Reever, & Bach-Peterson, 1980). 12 items are rated on 0-4 scale. Range: 0-48. No subscales. Higher scores represent worse outcomes; (b) Center for Epidemiological Studies Depression Scale (CES-D), a questionnaire measuring depression (Radloff, 1977). 20 items are rated on a 0-3 scale and summed (range = 0-60). There are no subscales. Higher scores represent worse outcomes. The clinical cut-off is usually set at a score of 16; (c) Beck Anxiety Inventory (BAI), a questionnaire measuring anxiety (Beck, Epstein, Brown, & Steer, 1988). 20 items are rated on a 0-3 scale and summed (range= 0-60). Higher scores indicate worse outcomes. There are no subscales. A score greater than 36 is considered to be clinically significant; and (d) Satisfaction with Life Scale, a questionnaire measuring overall life satisfaction and well-being (Diener, Emmons, Larsen, & Griffin, 1985). 5 items scored on a 1-7 scale and summed (Range = 5-35). Lower scores indicate worse outcomes. A score of 20 is considered neutral with higher scores considered increasingly more satisfied and lower scores considered increasingly more dissatisfied.

Contact initiated by study staff

Caregivers receive \$75 for completing the installation of the system in their homes and \$25 for each questionnaire they complete (initial questionnaire, 3-months, and 6-months). Qualtrics questionnaires will be sent via email to caregivers in both research conditions at baseline, 3 months, and 6 months. After participation, a member of the research team will contact the caregivers to let them know they are welcome to uninstall and dispose of the system (or mail it back with costs covered), or they may choose to keep any sensors, devices, or equipment.

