## Statistical Analysis Plan

### Primary Outcomes

All caregivers—regardless of randomized study condition—complete questionnaires on three separate occasions during this study: baseline, 3-months, 6-months. The four outcome measures include changes over the 6-month study period for the following scales: Zarit Burden Interview-Short Form, a questionnaire measuring caregiver burden (Zarit, Reever, & Bach-Peterson, 1980). 12 items are rated on 0-4 scale. Range: 0-48. No subscales. Higher scores represent worse outcomes; Center for Epidemiological Studies Depression Scale (CES-D), a questionnaire measuring depression (Radloff, 1977). 20 items are rated on a 0-3 scale and summed (range = 0-60). There are no subscales. Higher scores represent worse outcomes. The clinical cut-off is usually set at a score of 16; Beck Anxiety Inventory (BAI), a questionnaire measuring anxiety (Beck, Epstein, Brown, & Steer, 1988). 20 items are rated on a 0-3 scale and summed (range= 0-60). Higher scores indicate worse outcomes. There are no subscales. A score greater than 36 is considered to be clinically significant.; and Satisfaction with Life Scale, a questionnaire measuring overall life satisfaction and well-being (Diener, Emmons, Larsen, & Griffin, 1985). 5 items scored on a 1-7 scale and summed (Range = 5-35). Lower scores indicate worse outcomes. A score of 20 is considered neutral with higher scores considered increasingly more satisfied and lower scores considered increasingly more dissatisfied.

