### Statistical Methods

*Design:* Caregivers will be randomized into two groups: Active In-Home Technology System and Limited In-Home Technology System. Subjects will be randomized 1:1. Randomization of participants in each group will be determined by People Power employees. Analyses of caregiver health and well-being will use 2 X 3 (Condition [active treatment vs control] X Time [time 1 vs time 2 vs time 3]) mixed model analysis of variance. In all analyses, significant main effects and interactions will be decomposed using a priori or post hoc comparisons depending on whether they are hypothesized or not. Bonferroni corrections will be used to control for Type I error resulting from multiple comparisons. Statistical Power. Tests of hypothesized Group differences (active treatment vs control condition) for caregiver health and well-being will have .80 power to detect a medium effect size (one-tailed, alpha = .05). Using repeated measures analysis of variance, tests of the interaction of Condition (2 groups) X Time (3 assessments) will have power of .99 to detect a medium effect size (correlation between repeated measures  $r = .5$ , alpha = .05).

*Analysis:* Descriptive statistics will be used to summarize all the clinical characteristics and demographic outcomes. These will be summarized overall, by treatment group, by assessment time, and by treatment group and time. Continuous variables will be summarized using means, standard deviations, and ranges. Categorical data will be summarized by number and percent. To evaluate the treatment effects, we will use repeated measures ANOVAs. The other predictors will be treatment group, and time (baseline, 3-months, and 6-months for caregiver outcomes). To evaluate treatment effects, an interaction term between treatment group and time will be included

to examine treatment group-related differences in the assessments for each outcome. Each significant interaction will be followed up with paired t-tests to examine treatment differences at each set of time points. Although this study involves 4 outcomes, we do not plan formal multiple comparison adjustments if the results fit a coherent pattern that is consistent with the context of similar studies. In this case, each result will reinforce the other, rather than detracting from one another, as required by formal multiple comparisons adjustments such as Bonferroni.

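### Nothing in the plan requires the baseline questionnaire to be submitted before randomisation or shipment, so the time-1 score can be recorded after allocation or installation

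*Protocol*

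**What the plan says.** Three early steps are described in the protocol, each in relation to consent.

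- **Baseline link.** Under Initial Encounter, after consent for the person with dementia (own or surrogate), "caregiver participants will be sent a link to complete a set of questionnaires". Baseline Outcome Assessment repeats this: "Once consent procedures are complete, caregivers receive a Qualtrics link with their initial questionnaire".
- **Shipment.** The next sentence of Initial Encounter gives the same condition: "Once PWD consent is obtained, People Power will mail the Presence Caregiver system to the caregivers for self-installation".
- **Randomisation.** The Randomization section states: "Randomization of participants in each group will be determined by People Power employees after the consent process".

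The final section of the protocol pays caregivers $75 "for completing the installation of the system in their homes" and, separately, $25 per questionnaire. Neither payment depends on the other having been earned.

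The SAP relies on the baseline score. Under Primary Outcomes, "The four outcome measures include changes over the 6-month study period for the following scales". Under Statistical Methods the model is "Condition [active treatment vs control] X Time [time 1 vs time 2 vs time 3", with baseline as time 1, and the treatment test is the interaction: "To evaluate treatment effects, an interaction term between treatment group and time will be included".

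**The concern.** A baseline score serves as a reference for change only if it is taken before anything that differs between the arms can affect it. Here the questionnaire is emailed and answered when the caregiver chooses, while allocation and shipment are not stated to wait for it. No completion window is set, and there is no rule for a baseline that arrives late.

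All four outcomes are caregiver self-reports. A baseline completed after installation may already contain some benefit, or some burden from setting up the equipment. A baseline completed after allocation, by a caregiver who knows or guesses the arm, may contain a reaction to it. Either shift arises after randomisation and can differ by arm, so randomisation does not balance it. It then enters the Condition x Time test through time 1. Analysis cannot cleanly undo it: dropping late baselines afterwards would select caregivers on something that happened after allocation.

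**Working it through.** **1. Is there a gate?**

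| Step | Stated condition | Must baseline be submitted first? |
|---|---|---|
| Baseline link emailed | Consent complete | n/a |
| System mailed | Consent obtained | Not stated |
| Randomisation | After the consent process | Not stated |
| Installation payment | Installation completed | Not stated |

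For shipment, consent is the stated trigger. For randomisation it is only an earliest bound. In both cases the sequence consent, allocation, shipment, installation, baseline complies with the text as written.

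**2. The plan's own figure.** The SAP gives power of .99 for the interaction at a medium effect, r = .5 and alpha = .05. Taking medium as f = 0.25 (an assumption; the SAP gives no number), with N = 120 and m = 3 assessments:

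- lambda = f² x N x m / (1 − r) = 0.0625 x 120 x 3 / 0.5 = 45, with 2 and 236 df.
- Power exceeds .9999, which is consistent with the stated .99.

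**3. An effect in SD units.** To show what a late baseline does, the effect needs a shape over time. Assumptions:

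- The arms differ by D = 0.5 SD at both 3 and 6 months.
- A net fraction L of D is already present in the mean baseline difference.
- There is no shift in the control arm.
- n = 60 per arm, r = .5, equal variances and correlations, complete data, alpha = .05.

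The arm differences at the three times are (L·D, D, D). Their deviations from their mean are −2D(1 − L)/3, D(1 − L)/3 and D(1 − L)/3, with sum of squares (2/3)D²(1 − L)². Hence

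lambda = 2n x (1/4) x (2/3)D²(1 − L)² / (1 − r) = n D²(1 − L)² / [3(1 − r)].

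With L = 0 this is 60 x 0.25 / 1.5 = 10. That corresponds to f = √(10 x 0.5 / 360) = 0.118, well below 0.25, which is why the clean-baseline power below is lower than .99. In general lambda = 10(1 − L)², and the difference in change from baseline is 0.5(1 − L).

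| L | Difference in change (SD) | lambda | Interaction power |
|---|---|---|---|
| 0 | 0.500 | 10.0 | .81 |
| 0.05 | 0.475 | 9.025 | .77 |
| 0.10 | 0.450 | 8.1 | .72 |
| 0.20 | 0.400 | 6.4 | .61 |

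**4. What L stands for.** L is the share of active-arm caregivers with a late baseline multiplied by the fraction of the effect they already show. If 10% answer late with half the effect present, L = 0.10 x 0.5 = 0.05; if 20% do, L = 0.10. Neither component is in the documents.

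**5. Direction.** L need not be positive. If late active-arm baselines were worse than they should be, for example because of the effort of installation, L would be negative and change would be exaggerated. At L = −0.10 the difference in change would be 0.5 x 1.10 = 0.55 SD.

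**The case against.** The strongest reply is that the usual order is intended. Baseline Outcome Assessment comes before Randomization, the link is mentioned before the mailing, and randomising after baseline return is fully compatible with the wording. An emailed, paid questionnaire will also usually be completed before a mailed kit has arrived and been installed. This stands as a reason to expect few post-installation baselines. It does not supply a rule, and nothing would identify or exclude the exceptions.

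A second reply concerns allocation. The documents do not say whether caregivers know their arm. Both arms receive a system (active or limited), and the mailing sentence does not distinguish them. If the arm is neither disclosed nor inferred, a baseline completed after allocation but before installation is not biased by allocation. This also stands, and it narrows the exposure.

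A reader might go further and infer that consent itself triggers randomisation, that caregivers answer baseline knowing their arm, that baselines are in fact contaminated, or that the bias must be towards no effect. The text supports none of these. Two further consequences might be inferred but are not needed for this point. The SAP plans no baseline covariate, so adjustment for a post-randomisation baseline does not arise. The SAP's complete-response analysis is one of two sensitivity versions, and its weaknesses belong to missing data, not to sequence.

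**Conclusion.** The concern holds as a gap in sequence that the plan should close. As written, the protocol allows the time-1 score to be taken after allocation or installation, and the SAP's treatment test uses that score. The documents do not show that this happens, how often it would, or in which direction the net bias would run.

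The power loss from .81 to .77, .72 or .61 is an illustration under the assumptions listed with it, not an estimate for this trial, and it covers only the attenuating case. It does not show that the SAP's .99 is wrong, since that figure rests on a different effect size. The case for acting is that the safeguard is cheap and the bias cannot be cleanly removed afterwards.

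**What to change.** Amend Initial Encounter, Baseline Outcome Assessment and Randomization in the protocol to one fixed order: consent, baseline questionnaire submitted (confirmed by its Qualtrics time stamp), randomisation, shipment. State that no caregiver is randomised or sent a system until baseline has been submitted. Record the dates of baseline submission, randomisation and shipment for every caregiver, so that the order can be verified.

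If enrolment has begun, compare these dates for caregivers already randomised and report how many baselines came after allocation or shipment.

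The cost is a protocol wording change and one time-stamp check before each allocation. Slow responders wait a little longer for the system, and caregivers who never return baseline are not randomised, so somewhat more may need to be consented to reach 60 per arm. If this order is already followed in practice, the change only writes it down.

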## Statistical Analysis Plan

### Primary Outcomes

All caregivers—regardless of randomized study condition—complete questionnaires on three separate occasions during this study: baseline, 3-months, 6-months. The four outcome measures include changes over the 6-month study period for the following scales: Zarit Burden Interview-Short Form, a questionnaire measuring caregiver burden (Zarit, Reever, & Bach-Peterson, 1980). 12 items are rated on 0-4 scale. Range: 0-48. No subscales. Higher scores represent worse outcomes; Center for Epidemiological Studies Depression Scale (CES-D), a questionnaire measuring depression (Radloff, 1977). 20 items are rated on a 0-3 scale and summed (range = 0-60). There are no subscales. Higher scores represent worse outcomes. The clinical cut-off is usually set at a score of 16; Beck Anxiety Inventory (BAI), a questionnaire measuring anxiety (Beck, Epstein, Brown, & Steer, 1988). 20 items are rated on a 0-3 scale and summed (range= 0-60). Higher scores indicate worse outcomes. There are no subscales. A score greater than 36 is considered to be clinically significant.; and Satisfaction with Life Scale, a questionnaire measuring overall life satisfaction and well-being (Diener, Emmons, Larsen, & Griffin, 1985). 5 items scored on a 1-7 scale and summed (Range = 5-35). Lower scores indicate worse outcomes. A score of 20 is considered neutral with higher scores considered increasingly more satisfied and lower scores considered increasingly more dissatisfied.

### Statistical Methods

*Design:* Caregivers will be randomized into two groups: Active In-Home Technology System and Limited In-Home Technology System. Subjects will be randomized 1:1. Randomization of participants in each group will be determined by People Power employees. Analyses of caregiver health and well-being will use 2 X 3 (Condition [active treatment vs control] X Time [time 1 vs time 2 vs time 3]) mixed model analysis of variance. In all analyses, significant main effects and interactions will be decomposed using a priori or post hoc comparisons depending on whether they are hypothesized or not. Bonferroni corrections will be used to control for Type I error resulting from multiple comparisons. Statistical Power. Tests of hypothesized Group differences (active treatment vs control condition) for caregiver health and well-being will have .80 power to detect a medium effect size (one-tailed, alpha = .05). Using repeated measures analysis of variance, tests of the interaction of Condition (2 groups) X Time (3 assessments) will have power of .99 to detect a medium effect size (correlation between repeated measures  $r = .5$ , alpha = .05).

*Analysis:* Descriptive statistics will be used to summarize all the clinical characteristics and demographic outcomes. These will be summarized overall, by treatment group, by assessment time, and by treatment group and time. Continuous variables will be summarized using means, standard deviations, and ranges. Categorical data will be summarized by number and percent. To evaluate the treatment effects, we will use repeated measures ANOVAs. The other predictors will be treatment group, and time (baseline, 3-months, and 6-months for caregiver outcomes). To evaluate treatment effects, an interaction term between treatment group and time will be included

to examine treatment group-related differences in the assessments for each outcome. Each significant interaction will be followed up with paired t-tests to examine treatment differences at each set of time points. Although this study involves 4 outcomes, we do not plan formal multiple comparison adjustments if the results fit a coherent pattern that is consistent with the context of similar studies. In this case, each result will reinforce the other, rather than detracting from one another, as required by formal multiple comparisons adjustments such as Bonferroni.

Conversely, if only one or a very few measures reach statistical significance and their directions and/or magnitudes do not coherently fit with our a prior expectations, then we will note that the result(s) with  $p < 0.05$  lack plausibility and could be due to chance, despite meeting the conventional cutoff for statistical significance.

*Missing Data:* If subjects either cannot or refuse to complete surveys we will use a sensitivity analysis approach in dealing with these missing data by performing analysis with 2 versions of scores: 1) with missing item interpolated using mean replacement by group, and 2) only using responses with 0% missing data. If the results differ for the two approaches, then we will report on the differences.

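### The separately powered group-difference test is not tied to any assessment waves; if it is the Condition main effect, it averages in baseline, which shrinks a follow-up benefit and lets chance baseline imbalance through

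*SAP*

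**What the plan says.** All of this is in the SAP, Statistical Methods, unless noted.

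- The Design paragraph names one model, a "2 X 3 (Condition [active treatment vs control] X Time [time 1 vs time 2 vs time 3]) mixed model analysis of variance". The Analysis paragraph gives the Time levels as "time (baseline, 3-months, and 6-months for caregiver outcomes", so baseline is one of the three outcome waves.
- The Design paragraph also says "In all analyses, significant main effects and interactions will be decomposed using a priori or post hoc comparisons". Main effects are therefore to be followed up, not only interactions.
- The power statement makes two claims. The first covers "Tests of hypothesized Group differences (active treatment vs control condition) for caregiver health and well-being": .80 for a medium effect, one-tailed, alpha .05. It names no wave, model or correlation. The second covers the Condition by Time interaction: .99 for a medium effect, with a correlation of .5 between repeated measures.
- The Analysis paragraph names the interaction of treatment group and time as the term for evaluating treatment effects, and has follow-up comparisons after a significant interaction.
- SAP, Primary Outcomes, defines the four outcomes as changes over the six months.

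The available text describes no baseline-adjusted contrast and has no rule against reporting a significant Condition main effect as a treatment difference.

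**The concern.** In a 2 by 3 ANOVA, the test of group that is not the interaction is the Condition main effect: the difference between arms in the equally weighted mean of all three waves. If the group-difference claim refers to that test, there are two consequences.

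First, the baseline wave can carry no treatment effect, so averaging it in pulls the estimate towards zero. Second, whatever baseline difference randomization happens to produce is counted as part of the treatment difference. The outcomes are defined as changes, and a mean that includes baseline does not measure change.

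At stake is a second route to a treatment claim, beside the interaction, on each of four outcomes. That route is weak when the benefit is real, and open to misreading when the arms start out unequal.

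**Working it through.** **Inputs.** 60 caregivers per arm (Protocol, Randomization; the SAP gives a 1:1 ratio). Three waves, including baseline (SAP). Alpha .05, one-tailed (SAP, for the group test). Correlation r = .5 (SAP, stated for the interaction and carried over here).

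**Assumptions.** Medium means 0.5 SD. Variances and correlations are equal across waves. Everyone completes. The true arm difference is 0 at baseline and 0.5 SD at months 3 and 6. The Protocol says "Once consent procedures are complete, caregivers receive a Qualtrics link with their initial questionnaire" but does not give the order of that questionnaire and randomization; I take baseline as preceding any effect of the system.

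**1. The plan's .80.** Noncentral t, one-tailed, 0.5 SD:
- Simple two-group comparison at one wave: .86 at 60 per arm, .80 at 50 per arm.
- Three-wave main effect with 0.5 SD at every wave: standardised effect 0.5/√(2/3) = 0.612, power .95 at 60 per arm.

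The .80 is not reproduced at 60 per arm. It fits a simple two-group comparison of about 50 per arm, but the documents give no dropout figure that would lead there.

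**2. Condition main effect when baseline carries no effect.**
- Expected difference: (0 + 0.5 + 0.5)/3 = 0.333 SD, two-thirds of 0.5.
- Variance of a three-wave mean: (1 + 2r)/3 = 0.667, so its SD is 0.816.
- Standardised effect: 0.333/0.816 = 0.408.
- Power at 60 per arm: .72 one-tailed, .60 two-sided. Reaching .80 one-tailed takes 75 per arm.
- Other correlations (one-tailed/two-sided): r = .3 gives .80/.70; r = .7 gives .65/.53.
- If the effect builds up (0, 0.25, 0.5 SD), the expected difference is 0.25 SD, half the month-6 effect, and one-tailed power is about .51.

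**3. Alternatives, for 0, 0.5, 0.5 SD and r = .5.**

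| Test | Effect / SD | One-tailed | Two-sided |
|---|---|---|---|
| Condition main effect, three waves | 0.333/0.816 = 0.408 | .72 | .60 |
| Mean of months 3 and 6 | 0.5/√.75 = 0.577 | .93 | .88 |
| Same mean, adjusted for baseline | 0.5/√(.75 − .25) = 0.707 | .99 | .97 |

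The variance of the two-wave mean is (1 + r)/2 = .75; adjusting for baseline removes r² = .25.

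For the interaction F test, the noncentrality is (60/2) × Σ(difference − mean difference)²/(1 − r) = 30 × 0.1667/0.5 = 10, and power is .81. The SAP's .99 is not contradicted by this. It assumes a medium effect for the interaction itself (f = 0.25 gives noncentrality 120 × 0.0625 × 3/0.5 = 45), which is a larger departure than this scenario.

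**4. Baseline imbalance with no treatment effect, r = .5 (normal approximation).**
- SE of the baseline difference: √(2/60) = 0.183 SD. The chance of 0.3 SD or more in either direction is .10.
- Covariance of the three-wave mean with baseline is (1 + 2r)/3 = 0.667, so a 0.3 SD imbalance gives an expected main effect of 0.667 × 0.3 = 0.20 SD.
- SE of the main effect: √(0.667 × 2/60) = 0.149. Given the imbalance: √((0.667 − 0.444) × 2/60) = 0.086.
- One-tailed rejection when the imbalance favours the active arm: P(Z > (1.645 × 0.149 − 0.20)/0.086) = .30. Two-sided rejection: .14.
- The unadjusted mean of months 3 and 6, at the same imbalance: .20 and .11.

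Averaged over all randomizations, the main-effect test keeps its nominal level (.048 in simulation, one-tailed).

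**The case against.** The strongest answer is that the SAP already names another test for treatment effects. The interaction does not average baseline in, and a baseline difference that persists unchanged drops out of it. With power of .81 in the same scenario, it would usually detect the benefit. That stands. A reader might infer from the main-effect figures that the trial is likely to miss a real benefit, and the documents do not support that.

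A reader might also infer that the group-difference test simply is the Condition main effect, and that its .80 is therefore wrong. The SAP does not say so. The figure matches a single two-group comparison better than a three-wave main effect, so it may have been computed for some other test. What can be said is that the test is undefined.

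The imbalance argument has limits too. Overall type I error is not inflated. Any unadjusted comparison is sensitive to a chance imbalance, and the follow-up mean alone still gives 11% two-sided and 20% one-tailed at 0.3 SD. Much of the excess over 5% therefore comes from not adjusting, not from including baseline. The 30% applies only to a one-tailed test and an imbalance favouring the active arm.

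Finally, the loss of exactly one-third holds only if the effect is equal at both follow-ups, and the documents give no time course.

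None of this withdraws the commitment to decompose significant main effects, or tells the analyst which waves the group test uses.

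**Conclusion.** The concern holds in a conditional form. The SAP powers a group-difference test that it does not define, beside an interaction test that it does. On the most natural reading within the named model, the group test includes the baseline wave. A 0.5 SD effect equal at both follow-ups is then estimated at 0.333 SD, with one-tailed power of about .72 in place of the .93 or .99 available from the same questionnaires. A sizeable chance baseline difference could also be reported as a treatment difference.

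This does not invalidate the trial or its interaction test, and it does not show that overall alpha is exceeded. The sizes rest on 0.5 SD for medium, r = .5 with equal correlations, no effect at baseline and 60 completers per arm. The direction of the dilution rests only on baseline carrying no effect.

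**What to change.** In SAP, Statistical Methods:

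1. State that the Condition main effect over all three waves is not evidence of a treatment effect and will not be decomposed as one.
2. Define the group-difference test, for each outcome, as the active-minus-control difference in the mean of months 3 and 6, with that outcome's baseline score as covariate.
3. Replace the .80 with the power of that contrast, giving the effect size in SD, the correlation, the number analysed per arm and the sidedness. Under the assumptions above it is about .99 one-tailed and .97 two-sided at 60 per arm (.94 two-sided at 51 per arm).

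The cost is SAP wording and one contrast per outcome, with no new data. The small downside is that a caregiver without a baseline score drops out of the adjusted contrast unless the model handles it, so the SAP should say how.
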